7.4 Summary of Monitoring

Study Calendar: A summary of monitoring studies is provided in the following table:

Study Procedure	Treatment														Follow-up			
	Pre-infusion	Day 0	Wk 1	Wk 2	Wk 4/Day 0 [#2]	Wk 1 [#2]	Wk 2 [#2]	Wk 4 [#2]	Wk 6 [#2]	M 3	M 6	M 9	M 12	Y 2	Y 3	Y 4	Y 5	
STUDY DRUG ADMINISTRATION																		
mTAA CTL infusion		X			X													
DATA/TESTS/SPECIMENS TO BE OBTAINED																		
Blood Procurement ^a	X																	
Concomitant Medications		X																
PE	X				X													
Hx	X			X	X	X	X	X	X	X	X	X	X	X	X	X	X	
Pregnancy Test ^b	X																	
Blood Tests [Hematology, Comprehensive Metabolic Panel] ^c	X				X													
Imaging studies ^d	X								X									
Immune function studies ^e	X		X	X	X	X	X	X	X	X	X	X	X					
TCR deep-sequencing ^f																		
Tumor Biopsy ^g																		
DATA REVIEW																		
Eligibility Assessment for Procurement	X																	
Eligibility Assessment for Therapy		X																
Breast Cancer Information	X																	
AE Assessment		X ^h																
Response Assessment									X ⁱ									
Follow-up										X	X	X	X	X	X	X	X	
Follow-up Cancer																		
Follow-up Pregnancy																		
Relapse and Progression Assessment																		
Death																		

a- Blood will be collected for infectious disease testing, HLA typing, and mTAA CTL generation

TACTIC

Version 1.0 6/17/2016
Version 1.1 8/12/2016

Version 1.2 11/3/2016
Version 2.0 3/20/2017

Version 3.0 6/28/2017
Version 3.1 7/24/2017

Version 3.2 11/16/2017
Version 4.0 12/03/2018

Version 4.1 7/24/2019

- b- Pregnancy testing will be done pre-infusion in patients of childbearing potential. Either serum or urine is acceptable
- c- Hematology labs for CBC with differential WBC count; Comprehensive Metabolic Panel includes BUN, creatinine, bilirubin, SGOT, SGPT, alkaline phosphatase, sodium, potassium, chloride, carbon dioxide, albumin.
- d- Imaging studies required per section 7.3.3; imaging studies will be performed on a case by case basis to assess disease status at the discretion of the treating physician.
- e- Blood will be used for immune function assays including ELISPOT and cytotoxicity assays per section 7.2.4
- f- If required, TCR deep-sequencing will be performed to compare the infused product with the patient's peripheral blood per section 5.2
- g- Should the patient undergo a tumor biopsy at any time on the study, a sample will be used to determine the tumor antigen expression profile per section 7.2.6
- h- Adverse events are assessed throughout the clinical safety monitoring timeframe
- i- Time point for evaluation clinical efficacy, and eligibility for additional doses per section 5.2

TACTIC

Version 1.0 6/17/2016
Version 1.1 8/12/2016

Version 1.2 11/3/2016
Version 2.0 3/20/2017

Version 3.0 6/28/2017
Version 3.1 7/24/2017

Version 3.2 11/16/2017
Version 4.0 12/03/2018

Version 4.1 7/24/2019

Additional Treatment

Study Procedure	Treatment									Follow-Up			
	Day 0	Wk 1	Wk 2	Wk 4	Wk 6	M 3	M 6	M 9	M 12	Y 2	Y 3	Y 4	Y 5
STUDY DRUG ADMINISTRATION													
mTAA CTL infusion	X												
DATA/TESTS/SPECIMENS TO BE OBTAINED													
Concomitant Medications	X												
PE	X												
Hx	X		X	X	X	X	X	X	X	X	X	X	X
Pregnancy Test	X												
Blood Tests [Hematology, Comprehensive Metabolic Panel] ^a	X												
Imaging studies ^b					X								
Immune function studies ^c	X	X	X	X	X	X	X	X	X				
TCR deep-sequencing ^d													
Tumor Biopsy ^e													
DATA REVIEW													
AE Assessment	X ^f												
Response Assessment					X ^g								
Follow-up						X	X	X	X	X	X	X	X
Follow-up Cancer													
Follow-up Pregnancy													
Relapse and Progression Assessment													
Death													

a- Hematology labs for CBC with differential WBC count; Clinical chemistry panel includes sodium, potassium, carbon dioxide, chloride, blood urea nitrogen, creatinine, total bilirubin, alkaline phosphatase, aspartate transaminase, alanine transaminase)

b- Imaging studies are not required with additional doses but if performed the data will be collected.

c- Blood will be used for immune function assays including ELISPOT and cytotoxicity assays

d- If required, TCR deep-sequencing will be performed to compare the infused product with the patient's peripheral blood per section 5.2

e- Should the patient undergo a tumor biopsy at any time on the study, a sample will be used to determine the tumor antigen expression profile per section 7.2

f- Adverse events are assessed throughout the clinical safety monitoring timeframe

g- Data pertaining to clinical efficacy and safety monitoring will be obtained 6 weeks after the final injection per section 9.2

8.0 RESPONSE CRITERIA

A 6-week period after the second infusion will constitute a course, which will be evaluated for critical toxicity, and a 6-week period after the second CTL infusion will be required for evaluation for antitumor activity.

Patients with measurable disease will be assessed by standard criteria to determine clinical response. Evaluations of tumor size will be performed pre-infusion and 6 weeks after the second injection. Additional imaging performed as part of standard clinical care will also be evaluated. All patients who receive CTL infusion and continue to be enrolled on the study will be evaluable for response. Patient long term overall and progression free survival will also be evaluated at 1 year and then annually for up to an additional 4 years (total of 5 years follow-up).

8.1 Definitions

This study will use the RECIST 1.1 criteria

Definitions

Response and progression will be evaluated in this study using the international criteria proposed by the Response Evaluation Criteria in Solid Tumors (RECIST 1.1) Committee⁵¹. Changes in only the largest diameter (unidimensional measurement) of the tumor lesions are used in the RECIST criteria. Measurable lesions are defined as those that can be accurately measured in at least one dimension (longest diameter to be recorded) as >10 mm with CT scan, MRI, or clinically using calipers. The investigator will identify up to 5 measurable lesions to be followed for response. Serial measurements are to be done with CT or MRI. The same method of assessment is to be used to characterize each identified and reported lesion at baseline and during follow-up.

Complete Response: Disappearance of all target lesions

Partial Response (PR): At least a 30% decrease in the sum of the longest diameter (LD) of target lesions, taking as reference the baseline sum LD

Progressive Disease (PD): At least a 20% increase in the sum of the LD of target lesions, taking as reference the smallest sum LD recorded since the treatment started or the appearance of one or more new lesions

Stable Disease (SD): Neither sufficient shrinkage to qualify for PR nor sufficient increase to qualify for PD, taking as reference the smallest sum LD since the treatment started

9.0 STATISTICAL CONSIDERATIONS

This is a phase II study evaluating the safety and clinical efficacy of multiTAA-specific CTLs administered in patients with breast cancer. All patients will receive 2 injections at a fixed dose, 28 days apart, of T cells specific for all 5 tumor associated antigens.

9.1 Study Design and Sample Size

9.1.1 Sample Size

The primary endpoint is clinical benefit rate at 6 weeks after the second dose. Clinical benefit rate is defined as the proportion of evaluable patients with complete response or partial response or stable disease for ≥ 10 weeks from the first infusion (6 weeks after the second infusion) according to the RECIST criteria (see Section 8.4.1). This study is designed to detect an increase in clinical benefit rate from 5% to 30%. A Simon's two-stage optimal design will be employed to test the null hypothesis that clinical benefit rate is 5% vs. the alternative target rate of 30%. A sample of 9 evaluable patients will be accrued during the first stage. If none of these 9 patients shows clinical benefit at the analysis of the first stage, the study will be stopped early for lack of efficacy. If at least 1 patient shows clinical benefit, then a second stage will enroll additional evaluable patients. If we observe at least 3 clinical benefit responses out of the total of 17 evaluable patients enrolled into the study, we will consider further investigation is warranted. The proposed sample size is based on testing the above hypotheses with 90% power and 5% significance level. This design has 63% probability of stopping early and an expected sample size of 12 if the true clinical benefit rate is only 5%. Taking into account a 20% drop-out rate for non-evaluable patients, we propose to accrue a total of 22 patients.

9.2 Data Analysis

Safety and toxicity outcomes, and laboratory evaluations will be summarized using descriptive statistics. Information on the expansion, persistence and anti-tumor effects of the adoptively transferred tumor-specific CTL will be analyzed for the immunological parameters based on multimer analysis, intracellular cytokine staining and ELISpot assays to assess the frequency of cells secreting IFN γ using the descriptive statistics such as mean, median, standard deviation at each time point. Comparison of diagnostic imaging studies from pre-infusion to 6 weeks following the second infusion will be summarized. Frequencies, proportions and their 95% confidence intervals of clinical benefit responders (adjusted to account for the two-stage nature of the design) will be summarized overall. Overall survival and progression free survival will be estimated using the Kaplan-Meier survival curve and summarized by median and 95% confidence interval.

Growth curves of immune response over time within a patient will be generated to visualize general patterns of immune response. Pairwise comparisons will compare changes of these immunological parameters from pre-infusion to each time point of post-infusion measurements using paired t-tests or Wilcoxon signed-ranks tests. Longitudinal analysis is employed to model repeatedly-measured immunologic parameters. This will allow us to model patterns of immune response per patient while allowing for varying intercepts and slopes for a patient. The normality assumption will be assessed and transformations to achieve approximate normality will be carried out if necessary.

If a patient has stable disease or a partial response as assessed by the RECIST criteria (see Section 8.4.1) after the first two infusions, they may receive up to 6 additional infusions at monthly intervals. We will collect data on the survival, immunological efficacy and anti-tumor activity of cytotoxic T-lymphocyte lines after these additional infusions so it may be compared with results obtained after the initial two infusions.

TACTIC

Version 1.0 6/17/2016
Version 1.1 8/12/2016

Version 1.2 11/3/2016
Version 2.0 3/20/2017

Version 3.0 6/28/2017
Version 3.1 7/24/2017

Version 3.2 11/16/2017
Version 4.0 12/03/2018

Version 4.1 7/24/2019

To obtain preliminary data on the clinical efficacy and safety monitoring, patients will be monitored for 6 weeks after the final injection for toxicity using standard NIH criteria. If a patient develops Grade III-IV toxicity attributable to the CTL infusions at any time during the extended dosing regimen, they will not be able to receive any more CTL infusions.

9.3 Analysis Set

Evaluable for response: Only patients who receive both infusions will be evaluable for response.

Evaluable for adverse events: All patients who received the first infusion will be evaluable for adverse events.

9.4 Stopping Rule

If there are 2 patients with grade 4 events considered possibly related to the study drug, the study will be halted for review by the Data Safety Monitoring Committee and the FDA.

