3.3 Targeting EBV negative lymphomas using adoptive T cell transfer

To target lymphoma we have developed a strategy to target multiple tumor expressed antigens including PRAME, SSX2, MAGE-A4, NY-ESO-1 and Survivin.

To date we have infused a total of 18 patients: 9 with Hodgkin lymphoma, 8 with aggressive non-Hodgkin lymphoma, and 1 with a composite lymphoma. Patients have received 2 infusions of cells ranging from $0.5-2 \times 10^7$ multiTAA-T cells/m² without adverse events. Of 11 patients who were infused as adjuvant therapy all but 1 remain in remission (range 1-24 months post-infusion). Seven patients have received multiTAA-specific T cells to treat active disease. Of these, 1 had transient disease stabilization followed by disease progression, 3 have stable disease 3-6 months post-multiTAA-specific T cells while the remaining 3 (all with HL) have had complete responses, as assessed by PET. Notably, since patients received no pre-infusion cytoreductive chemotherapy, these clinical responses can be attributed to the cells infused. Indeed, clinical benefit correlated with the detection of tumor-reactive T cells in patient peripheral blood post-infusion directed against both targeted antigens as well as non-targeted TAAs including MAGEA2B and MAGE C1, indicating antigen spreading. Thus, infusion of autologous multiTAA-targeted T cells directed to PRAME, SSX2, MAGEA4, NY-ESO-1 and Survivin has been safe and provided clinical benefit to patients with lymphomas.

Additionally, we have administered these multi-antigen-targeted T cell lines to patients with multiple myeloma (n=5) and a spectrum of solid tumors including squamous cell carcinoma, lung cancer and osteosarcoma (n=4).

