At the end of the culture period, CTLs will be cryopreserved and aliquots tested for phenotype, function, specificity, identity and sterility. The frequency of tumor-specific CTLs will be determined using intracellular cytokine staining, ELISpot assay, and HLA-peptide tetramers if available. Effector memory phenotype and T cell subsets will be analyzed by flow cytometry.

Products that meet study specific release criteria, as detailed on the CofA, will be infused as per Section 5.2.

If a positive sterility testing result is reported after the product was infused, the FDA and other relevant parties would be notified as per manufacturing SOP B01.03.XX (Product Quality Assurance Program and Release and Return of Clinical GMP/GTP Products) and clinical research SOP J02.06.XX (Serious Adverse Experience and Unanticipated Problem

TACTIC

Version 1.0 6/17/2016
Version 1.1 8/12/2016

Version 1.2 11/3/2016
Version 2.0 3/20/2017

Version 3.0 6/28/2017
Version 3.1 7/24/2017

Version 3.2 11/16/2017
Version 4.0 12/03/2018

Version 4.1 7/24/2019

Reporting). Our management of such a situation is further described in our SOP F05.09.XX (Management of Culture Positive Cell Therapy Products).

We will use pepmixes produced by JPT Technologies as an antigen source. These pepmixes are overlapping peptide libraries (15 mers overlapping by 11 amino acids) spanning the entire sequence of each of the antigens of interest as per our lymphoma (TACTAL) study.

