10.0 MODIFIED FOLLOW-UP AND OFF STUDY CRITERIA

10.1 Criteria for Modified Follow-Up

The following criteria will result in the patient being ineligible for further treatment on the protocol, although response data will continue to be collected as applicable.

- 10.1.1 Any patient who develops grade \geq III infusional and/or organ toxicity that is NOT (1) pre-existing, or (2) due to infection or (3) due to underlying malignancy and is considered to be possibly, probably, or definitely related to the study drug. In such patients, the toxicities will be followed until resolution or their off-study date. Although no toxicity has been associated with the infusion of this product in patients with Hodgkin and non-Hodgkin lymphoma, we will actively look for evidence of any adverse events, such as cytokine release syndrome.
- 10.1.2 Any patient who receives any other hematopoietic progenitor cell product. In such patients, adverse event data collection will cease.
- 10.1.3 Any patient who receives therapy for progression of their breast cancer. In such patients, adverse event data collection will cease.
- 10.1.4 Any patient who desires to withdraw from the study or if the physician feels that it is in the best interest of the patient, treatment will be discontinued.

Patients who meet modified follow-up criteria remain on long-term follow-up as per the Summary of Monitoring (see table in Section 7.3.1)

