16.0 Appendix I - Grading of CRS**CRS Grading Scale**

Grade	Symptoms
1	
 Symptoms are not life threatening and require symptomatic treatment only (e.g. fever, nausea, fatigue, headache, myalgia, malaise)
2	
 Symptoms require and respond to moderate intervention Oxygen requirement <40% or hypotension responsive to fluids or low dose of one vasopressor or Grade 2 organ toxicity
3	
 Symptoms require and respond to aggressive intervention Oxygen requirement \geq 40% or hypotension requiring high dose or multiple vasopressors or Grade 3 organ toxicity or Grade 4 transaminitis
4	
 Life-threatening symptoms Requirements for ventilator support or Grade 4 organ toxicity (excluding transaminitis)
5	
 Death

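### One treatment-related death does not trigger the Section 9.4 halt, which needs two patients and names only grade 4

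*Combined protocol and SAP*

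**What the plan says.** Section 9.4 reads: "If there are 2 patients with grade 4 events considered possibly related to the study drug, the study will be halted for review". The reviewers are the Data Safety Monitoring Committee and the FDA. No other study-level safety trigger appears in the protocol.

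For cytokine release syndrome, Appendix I describes grade 4 as life-threatening, with the criterion "Requirements for ventilator support or Grade 4 organ toxicity (excluding transaminitis)". Death is the next row, grade 5.

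The other safety provisions act on one patient or on reporting:

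- Section 10.1 opens with "The following criteria will result in the patient being ineligible for further treatment on the protocol". Item 10.1.1 then covers grade III or higher toxicity and spells out three attribution levels, from possible to definite.
- The end of Section 9.2 stops further infusions for a patient with attributable grade III-IV toxicity during extended dosing.
- Section 10.2.4 lists death as a reason for that patient to leave the study.
- Serious events go to an SOP, named in 5.1 as "clinical research SOP J02.06.XX (Serious Adverse Experience and Unanticipated Problem" Reporting and cited again in 12.3.4. Its content is not included.
- Section 14.0 cites outside monitoring plans, also not included.

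**The concern.** A halt rule exists so that a pause after a serious signal does not depend on anyone's discretion. As written, 9.4 treats a related death no more strictly than a reversible grade 4 event, and on its literal wording less strictly.

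The supporting safety experience is small. Section 3.3 says "To date we have infused a total of 18 patients" and reports no adverse events at 0.5-2 × 10^7 cells/m². This trial uses the top of that range in a new population. Section 6.2 permits 2 + 6 = 8 infusions for patients with stable disease or partial response. The protocol itself warns of cytokine release after conventional antigen-specific T cells (3.5) and of damage to normal tissue from T cells against overexpressed antigens such as Survivin, one of the five targets (3.1). At stake is whether further patients are infused before anyone is obliged to review a first related death.

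**Working it through.** **Step 1. The rule applied to one related death.** The threshold is 2 patients (9.4).

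| Reading of 9.4 | Count from one grade 5 patient | Halt? |
|---|---|---|
| Literal: grade 4 only | 0 | No |
| Generous: grade 4 or worse, at least possibly related | 1 | No |

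The generous reading cures the grade and attribution wording but not the patient count. This conclusion needs no assumed rate.

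**Step 2. Inputs for the size.** Section 9.4 states no operating characteristics, so there is no plan figure to reproduce. The number infused is at most N = 22, the accrual in 9.1.1: 17/(1 − 0.20) = 21.25, rounded up. Assumed, because the documents give no rates: a related-death rate q of 1%, 2% or 5% per infused patient; a non-fatal related grade 4 rate r of 0% or 5%; independent patients; each outcome known before the next patient is infused; and no discretionary pause. The generous reading is used throughout.

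**Step 3. Formulas.**

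- P(at least one related death) = 1 − (1 − q)^N, ignoring any halt
- P(a related death and never halted) = N × q × (1 − q − r)^(N − 1)
- For r = 0, mean further patients infused after the first death = 1/q − N(1 − q)^(N − 1) / [1 − (1 − q)^N]

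For q = 1%, N = 22, r = 0:

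- 1 − 0.99^22 = 0.198
- 22 × 0.01 × 0.99^21 = 0.178
- 100 − 17.81/0.1984 = 10.2

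| Quantity | q = 1% | q = 2% | q = 5% |
|---|---|---|---|
| At least one related death, N = 22 | 0.198 | 0.359 | 0.676 |
| Death and never halted, N = 22, r = 0 | 0.178 | 0.288 | 0.375 |
| Death and never halted, N = 22, r = 5% | 0.060 | 0.096 | 0.120 |
| Death and never halted, 9 infused, r = 0 | 0.083 | 0.153 | 0.299 |
| Mean further patients infused, N = 22, r = 0 | 10.2 | 9.9 | 8.9 |
| Mean further patients infused, N = 22, r = 5% | 6.0 | 5.9 | 5.4 |

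The last row comes from 400,000 simulated trials. A trial in which the death is itself the second qualifying event counts as zero further patients.

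**Step 4. What the earlier experience rules out.** With 0 events in 18 patients, the one-sided 95% upper bound is 1 − 0.05^(1/18) = 0.153. Section 3.3 also mentions 5 + 4 = 9 other recipients without giving their safety results. If all were event-free, the bound would be 1 − 0.05^(1/27) = 0.105. These bounds are for any adverse event, not for death. They show how little is known and do not support any particular q.

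**The case against.** **Outside safeguards.** The monitoring plans in 14.0 and the serious-event SOP may require a pause after a fatal related event, and 9.4 does not forbid an earlier one. At a single treatment centre (6.7), it is hard to imagine nobody reacting. This stands as a limit on the consequence: the figures for further patients infused describe the written rule alone. It does not change what 9.4 requires.

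**Zero grade 4 events is the worst case.** A product that kills some patients but causes no non-fatal grade 4 event is unlikely. This also stands. At r = 10%, the chance of a related death with no halt is 22q(0.90 − q)^21, or about 2%, 3% and 4%. The existing rule would then catch most such trials.

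**Stage 1 is not 9 infused patients.** It is 9 evaluable patients (9.1.1), and 9.3 requires both infusions for response evaluation. A patient who dies after the first infusion is not evaluable, so stage 1 would infuse more than 9. The 9-infused row is therefore only a lower-end illustration.

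**Some deaths do count on the literal reading.** A patient who is ventilated before dying has passed through grade 4 and counts as one of the two. That is correct, but one is still below two.

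**Attribution will be hard.** Section 4.3.1 enrols patients with progressive disease after at least two prior lines, so some deaths from cancer may be called possibly related. That is a real cost of the change, quantified with the fix.

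**Conclusion.** The concern holds. Under either reading of 9.4, one related death with no other qualifying patient does not halt the study, and nothing else written in the protocol does so. That follows from the text alone.

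The size depends on assumed rates. For 22 infused patients and related-death rates of 1% to 5%, the chance of a related death that never triggers the halt is 18% to 37% without other grade 4 events, and 6% to 12% if 5% of patients have one. The finding concerns the rule in this protocol. The cited monitoring plans and SOP could narrow the gap in practice. It should be corrected because it bears on patient safety and the correction is small.

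**What to change.** Replace the single sentence in 9.4 with two triggers, each leading to a halt and review by the Data Safety Monitoring Committee and the FDA:

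- (a) any one grade 5 event considered at least possibly related to the cells and not due to the underlying malignancy, an exclusion that 10.1.1 already uses;
- (b) two patients with grade 4 or higher events considered at least possibly related.

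This takes a short amendment and no new data, since deaths and adverse events are already recorded (11.0 and 12.2). The price is some unneeded pauses. If 1% of infused patients die of progression and are wrongly judged possibly related, 1 − 0.99^22 = 20% of 22-patient trials would pause at least once; at 2% it is 1 − 0.98^22 = 36%. A pause is a review, not termination.
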